5.0 EMERGENCY UNBLINDING

Only in the event of a serious adverse event wherein the investigator feels that the patient cannot be adequately treated without knowing the identity of the study medication may the medication code be broken for a particular subject. If emergency un-blinding is required, [REDACTED] must be contacted as soon as possible. The Study Chair or Vice-Chair will log onto the Sharp Clinical Services website, unblind the patient, and contact the site investigator with the drug or placebo information. In the event of un-blinding, the patient will be removed from protocol therapy.

[figure not shown]
6.0 DRUG INFORMATION

6.1 Carvedilol (IND exempt, Coreg®, NSC #751177)

(06/28/17)

6.1.1 Source and Pharmacology:

Carvedilol is a racemic mixture in which nonselective β -adrenergic blocking activity is present in the S(-) enantiomer and with α 1-blocking activity is present in both R(+) and S(-) enantiomers at equal potency. Carvedilol has no intrinsic sympathomimetic activity. It is (\pm)-1-(Carbazol-4-yloxy)-3-[[2-(o-methoxyphenoxy)ethyl]amino]-2-propanol. Carvedilol is a racemic mixture with the following structure:

Carvedilol is a white to off-white powder with a molecular weight of 406.5 and a molecular formula of C₂₄H₂₆N₂O₄. It is freely soluble in dimethylsulfoxide; soluble in methylene chloride and methanol; sparingly soluble in 95% ethanol and isopropanol; slightly soluble in ethyl ether; and practically insoluble in water, gastric fluid (simulated, pH 1.1), and intestinal fluid (simulated, without pancreatin, pH 7.5).

Pharmacokinetics: Carvedilol is rapidly and extensively absorbed following oral administration, with absolute bioavailability of approximately 25% to 35% due to a significant degree of first-pass metabolism. Following oral administration, the

apparent mean terminal elimination half-life of carvedilol generally ranges from 7 to 10 hours. Plasma concentrations achieved are proportional to the oral dose administered. When administered with food, the rate of absorption is slowed, as evidenced by a delay in the time to reach peak plasma levels, with no significant difference in extent of bioavailability.

Carvedilol is extensively metabolized. Following oral administration of radiolabelled carvedilol to healthy volunteers, carvedilol accounted for only about 7% of the total radioactivity in plasma as measured by area under the curve (AUC). Less than 2% of the dose was excreted unchanged in the urine. Carvedilol is metabolized primarily by aromatic ring oxidation and glucuronidation. The oxidative metabolites are further metabolized by conjugation via glucuronidation and sulfation. The metabolites of carvedilol are excreted primarily via the bile into the feces. Demethylation and hydroxylation at the phenol ring produce 3 active metabolites with β -receptor blocking activity. Based on preclinical studies, the 4'-hydroxyphenyl metabolite is approximately 13 times more potent than carvedilol for β -blockade.

Compared to carvedilol, the 3 active metabolites exhibit weak vasodilating activity. Plasma concentrations of the active metabolites are about one-tenth of those observed for carvedilol and have pharmacokinetics similar to the parent. Carvedilol undergoes stereoselective first-pass metabolism with plasma levels of R(+)-carvedilol approximately 2 to 3 times higher than S(-)-carvedilol following oral administration in healthy subjects. The mean apparent terminal elimination half-lives for R(+)-carvedilol range from 5 to 9 hours compared with 7 to 11 hours for the S(-)-enantiomer.

The primary P450 enzymes responsible for the metabolism of both R(+) and S(-)-carvedilol in human liver microsomes are CYP2D6 and CYP2C9 and to a lesser extent CYP3A4, 2C19, 1A2, and 2E1. CYP2D6 is thought to be the major enzyme in the 4'- and 5'-hydroxylation of carvedilol, with a potential contribution from 3A4. CYP2C9 is thought to be of primary importance in the O-methylation pathway of S(-)-carvedilol.

Carvedilol is subject to the effects of genetic polymorphism with poor metabolizers of debrisoquin (a marker for cytochrome P450 2D6) exhibiting 2- to 3-fold higher plasma concentrations of R(+)-carvedilol compared to extensive metabolizers. In contrast, plasma levels of S(-)-carvedilol are increased only about 20% to 25% in poor metabolizers, indicating this enantiomer is metabolized to a lesser extent by cytochrome P450 2D6 than R(+)-carvedilol. The pharmacokinetics of carvedilol do not appear to be different in poor metabolizers of S-mephenytoin (patients deficient in cytochrome P450 2C19).

Carvedilol is more than 98% bound to plasma proteins, primarily with albumin. The plasma-protein binding is independent of concentration over the therapeutic range. Carvedilol is a basic, lipophilic compound with a steady-state volume of distribution of approximately 115 L, indicating substantial distribution into extravascular tissues. Plasma clearance ranges from 500 to 700 mL/min.

Pregnancy: There are no adequate and well-controlled studies in pregnant women.

6.1.2 Toxicity

Incidence	Toxicities
Common (>20% of patients)	
 • Fatigue • Dizziness
Occasional (4-20% of patients)	
 • Hypotension • Pain in chest • Bradycardia • Shortness of breath • Generalized edema • Peripheral edema • Syncope • Headache • Nausea • Diarrhea • Weight gain • Hyperglycemia • Dry mouth • Insomnia • Blurred vision • Anxiety • Concentration impairment
Rare (<3% of patients)	
 • Paresthesia • Muscle cramps • Blurred vision • Impotence • Insomnia • Anemia • Thrombocytopenia • Hypersensitivity reaction • Stevens-Johnson syndrome or toxic epidermal necrolysis
Pregnancy & Lactation	
Females of childbearing age should avoid pregnancy while taking study medication and for two months after discontinuation. The use of barrier or other contraceptive measures is strongly recommended during the study period and for two months thereafter.
 
It is not known if carvedilol is excreted in breast milk. Due to the potential for serious adverse reactions in the nursing infant, the manufacturer recommends a decision be made whether to discontinue nursing or to discontinue the drug, taking into account the importance of treatment to the mother.

6.1.3 Formulation and Stability:

Carvedilol 3.125 mg, 6.25 mg capsules, and matching placebo will be shipped at room temperature. The capsules should be stored at a controlled room temperature of 20-25°C (68-77°F) in the 3-month supply kits. Temperature excursions up to

30°C are allowed without concern for stability of the drug. Carvedilol or matching placebo will be stored and dispensed in the original containers.

6.1.4 Guidelines for Administration:

See Treatment and Dose Modification sections of the protocol, [Section 4.0](#).

6.1.5 Supplier:

Carvedilol is available in 3.125 mg, 6.25 mg, 12.5 mg, and 25 mg tablets. For this trial, generic 3.125 mg and 6.25 mg capsules and matching placebo capsules will be manufactured by Sharp Clinical Services (Phoenixville, PA). **Do not use commercial supply.**

6.1.6 Obtaining the Agent:

Agent Ordering:

Distribution of study drug will be performed by a third party at Sharp Clinical Services. Details regarding drug randomization and distribution are on the study web page (see “Study Drug Packet”).

Agent Returns:

All unused or expired study drug should be destroyed per institutional guidelines.

6.1.7 Drug Interactions:

The following drugs have been reported as inhibitors or inducers of CYP2D6 which is the major P450 enzyme that metabolizes carvedilol. Concomitant use of strong and clinically significant moderate inhibitors will not be allowed while on study.

Strong CYP2D6 inhibitors

(not allowed on study):

bupropion
fluoxetine
paroxetine
quinidine

Clinically significant

moderate CYP2D6 inhibitor

(not allowed on study):

duloxetine

Other moderate CYP2D6 inhibitors

(should be avoided while on study):

cinacalcet
mirabegron
terbinafine

Weak CYP2D6 inhibitors

(should be avoided while on study):

amiodarone
cimetidine
thioridazine

Other possible CYP2D6 inhibitors

(will be tracked on study):

celecoxib
chlorpheniramine*
chlorpromazine
citalopram
clemastine *
clomipramine

desvenlafaxine
diphenhydramine *
doxepin
doxorubicin
escitalopram
halofantrine
haloperidol
hydroxyzine *
labetolol
levomepromazine
lopinavir
methadone
metoclopramide
midodrine
moclobemide
perphenazine
ranitidine *
ritonavir
ticlopidine
tipranavir
tripeleennamine
sertraline
vemurafenib
other histamine H1 receptor
antagonists**

Possible CYP2D6 inducers

(will be tracked while on study):

dexamethasone
rifampin

Virtually no effect on CYP2D6:

venlafaxine (Effexor) – *preferred*
antidepressant while on study

*Available over the counter

**Examples: cetirizine, dimenhydrinate, doxylamine, fexofenadine, loratidine, meclizine, pheniramine

7.0 EVALUATIONS/MATERIAL AND DATA TO BE ACCESSIONED

Timing of protocol therapy administration, response assessment studies, and surgical interventions are based on schedules derived from the experimental design or on established standards of care. Minor unavoidable departures (up to 72 hours) from protocol directed therapy and/or disease evaluations (and up to 1 week for surgery) for valid clinical, patient and family logistical, or facility, procedure and/or anesthesia scheduling issues are acceptable per COG administrative Policy 5.14 (except where explicitly prohibited within the protocol).

7.1 Required Clinical, Laboratory and Disease Evaluations

Studies	PRIOR to Enrollment	Days on Study Drug										
	Eligibility Screening	1 st day of drug	14 ±2 calendar days	42 ±7 calendar days	90 [@]	180	270	365	455	540	630	730
History and physical	X		X	X	X [@]	X		X		X		X
Cardiac Evaluations												
Echocardiogram ^{&}	X					X		X		X		X
Electrocardiogram	X		X	X								
Lab Tests												
Pregnancy Test [*]	X											
Hematocrit Blood Draw	X											
Biomarkers Blood Draws (see Section 10.3)	X					X		X		X		X
CBC and Comprehensive Metabolic Panel (Creatinine, liver panel (bilirubin, AST/ALT))	X					X		X		X		X
Questionnaires (available in English and Spanish)												
Demographics, Medical and Family History Forms	X											
HRQoL Form	X					X		X		X		X
Treatment Management and Adherence Monitoring												
Follow-up phone call [#]					X [@]		X		X		X	
Symptom Log, Study Tablet dispersal		X	X	X	X	X	X	X	X	X	X	X [%]

& COG institutions will receive additional per-case reimbursement for this study to allow institutions to pay for the two echocardiograms (month 6 and month 18) that are not considered standard of care.

[@] For the Day 90 visit only, the patient has the option to do an in-person visit or a phone follow up, depending on their ability to easily return to the clinic. If Day 90 is a phone follow up, the History and Physical is not required.

^{*} Women of childbearing potential require a negative pregnancy test prior to starting study drug; females of reproductive potential may not participate unless they have agreed to use an effective contraceptive method during the study and for at least 2 months after the last dose of study drug. Abstinence is an acceptable method of birth control. For female participants of childbearing age, investigators will follow-up regarding their pregnancy status at each clinic visit. A pregnancy test is required at the eligibility screening and then throughout the study period as deemed necessary by the investigator.

[#] Follow-up phone calls are to confirm medication tolerance after the screening day and in-between clinic visits to determine (and reinforce) adherence, complete the Symptom Log, and arrange medication refill. The medication refills are either picked up by the patient or sent via FedEx to their home.

[%] No study medication is dispensed at Day 730.

8.0 CRITERIA FOR REMOVAL FROM PROTOCOL THERAPY AND OFF STUDY CRITERIA

8.1 Criteria for Removal from Protocol Therapy

- a) Physician determines it is in the patient's best interest.
- b) Inability to tolerate dose escalation from level 1 to level 2.
- c) Treatment interruption longer than 90 consecutive days.
- d) A cardiac event (see [Section 8.1.1](#) for definition).
- e) Pregnancy.
- f) Adverse Event requiring removal from protocol therapy (see [Section 13.4](#)).
- g) Diagnosis of a new malignancy requiring systemic chemotherapy or radiation.
- h) Adherence < 50% in any 90 day period.
- i) Emergency un-blinding (see [Section 5.0](#))
- j) Study is terminated by Sponsor.

Patients who are taken off protocol therapy do not require any additional study observations/evaluations unless they experienced a cardiac event or have become pregnant.

8.1.1 Study End Form

All patients withdrawn from study medication must have the reason for withdrawal recorded on the Study End Form located on the ALTE1621 webpage on the COG website (including subjects who complete the study). All adverse events leading up to withdrawal of study medication must be fully documented and followed up as appropriate. To ensure that all withdrawals due to adverse events are correctly identified, "Adverse Event" should only be marked as the reason for withdrawal on the Study End Form for those patients whom an adverse event was considered to have been the direct cause of withdrawal from the study medication. This is particularly important when adverse events are ongoing at the time of withdrawal, but the reason for withdrawal is not related to the adverse event.

A cardiac event is defined as: 1) acute heart failure with pulmonary edema and S3 gallop without obvious correctable cause (i.e., intravenous fluid overload during surgery), or 2) EF < 50%, shortening fractional (SF) < 25% or a 20% drop from an earlier test. Subjects who develop a cardiac event while on study will be referred to a cardiologist for proper diagnostic work-up and management. These individuals will be taken off study drug.

Participants must not be planning to become pregnant for two years to be eligible for the study, and they will be warned about the importance of not becoming pregnant while on study at the time of enrollment. They will be advised to use contraception for all sexual activity during the course of the study and for 2 months afterwards. Nevertheless, occurrence of an unplanned intrauterine pregnancy while on study will be an indication for immediately stopping treatment and the patient must withdraw from the study. If the patient should become pregnant while on study, or within 2 months after discontinuing therapy, her treatment assignment will be unblinded immediately (see [Section 5.0](#)). Whenever possible, a pregnancy should be followed to term, any premature terminations reported, and the status of the mother and child should be reported to the study team after delivery.

8.2 Off Study Criteria

- a) Withdrawal of consent for any further data submission.
- b) Death.
- c) Completion of planned study assessments.
- d) Lost to follow up (defined as no contact with patient for ≥ 90 consecutive days after a required observation).

9.0 STATISTICAL CONSIDERATIONS

The following section includes the protocol that was active at the time of study initiation and amendments that were made resulting from a reduction in study sample size from 125 per arm to 91 per arm. With Amendment #4, revisions were made to the detectable treatment effect size and interim analyses. The analysis plan remains the same.

9.1 Study Design

This is a Phase 2b randomized double-blind placebo controlled clinical trial to examine the effect of carvedilol on preventing cardiovascular morbidity/mortality associated with anthracycline exposure during childhood cancer treatment. Childhood cancer survivors who were previously treated with ≥ 250 mg/m² cumulative dose of anthracyclines will be randomized 1:1 between the 2 arms: carvedilol arm and the placebo arm. Randomization will be stratified by age at diagnosis (2 strata: < 5 years, ≥ 5 years), time since diagnosis (2 strata: < 10 years, ≥ 10 years), and cardiac irradiation (2 strata: any, none), as stratification factors (8 strata total) and a block size of 4. Daily treatment with carvedilol and placebo will continue for 2 years. Cardiovascular functions will be assessed at baseline and semi-annually. The primary endpoint is LV thickness-dimension ratio (LV T-D) derived from echocardiogram.

9.2 Patient Accrual and Expected Duration of the Trial

It is estimated that approximately 50-60% of the 450,000 survivors of childhood cancer who are alive in the U.S. today have received anthracyclines. Many pediatric cancer patients (approximately 20-25%) are being treated with anthracyclines with cumulative dose ≥ 250 mg/m², such as those with bone cancer and AML. Although exact estimates are not available, using the conservative estimates of 50% and 20% to calculate, $>30,000$ survivors would meet the current eligibility criteria. We expect thousands of childhood cancer survivors meeting such criteria are currently being followed at member COG institutions.

ACTIVATION PROTOCOL:

To answer the scientific questions, 250 randomized subjects (125 per arm) is required. Through a different mechanism, 82 patients have already been accrued and randomized. Therefore, this COG protocol aims to enroll and randomize an additional of 168 patients through this protocol, with a maximum accrual of 177 patients to account for up to 5% of ineligible enrollments. Given the large pool of potential eligible patients, we expect to complete the accrual, including the time it takes to open the study at COG institutions, over 4 years.

WITH AMENDMENT #4:

To answer the scientific questions, 182 subjects (91 per arm) who are randomized and start study drug are required. Through a different mechanism, 87 patients have already been accrued and randomized. Therefore, this COG protocol aims to enroll, randomize and start

treatment for an additional **95** patients through this protocol. To account for attrition, enrollment through this COG trial may proceed up to 109 patients. Given the large pool of potential eligible patients, we expect to complete the accrual, including the time it takes to open the study at COG institutions, over 5 years.

9.3 Data Analytic Plan

Aim 1.1: To determine the impact of a two-year course of low-dose carvedilol on surrogate echocardiographic indices of heart failure (HF) risk.

9.3.1 LV Thickness-Dimension Ratio (LV T-D)

The primary endpoint of this trial is LV thickness-dimension ratio (LV T-D) z-score. LV thickness is reported in terms of LV posterior wall dimension in systole, while LV dimension will be based on the internal diameter in diastole. Z-scores will be calculated using the formula: $(LVPWD / LVEDD - 0.18) / 0.025$.²¹

LV T-D Z-score will be determined at baseline, 6 months, 12 months, 18 months and 24 months. The z-scores will be appropriately transformed to normality as necessary. The analysis will be conducted accounting for correlation among repeated measurements within individuals. This may be done using the Generalized Estimating Equation (GEE) approach or by the restricted maximum likelihood estimation (REML) approach with the mixed effect model with random effects. Various covariance structures will be assumed, including the unstructured, compound symmetry, and autoregressive lag-1 correlation. GEE and REML will be implemented using GENMOD and MIXED procedures in SAS.

LV T-D z-scores will be modeled as a linear function of time. Under the intention-to-treat principle, the efficacy of carvedilol will be examined by comparing the slopes of the longitudinal linear models of LV T-D z-score between carvedilol and placebo control group. The difference in slopes by treatment group will be introduced by including an interaction term of time with group indicator (0 for placebo, 1 for carvedilol). Treatment effect will be tested by a 1-df test for the interaction. Non-linear effects will be tested by including an interaction of a quadratic term in time with the group indicator.

To examine other than the linear model, we will also fit an unstructured mean model, which is a non-parameterized model with four indicator variables of time. Interactions of the time and group indicators will be included to allow for treatment differences at follow-up time points. This will enable us to examine other than linear or quadratic trends in time.

Because of randomization, we expect no difference between the expected values of LV T-D z-scores at t0 between the treatment groups. However, we will evaluate the success of the randomization by examining between-group differences in demographic and clinical characteristics (i.e. age at anthracycline exposure, chest radiation, time from treatment), study site, as well as the mean LV T and D z-scores at baseline. If imbalance is evident, our analysis will take into account the covariates with significant imbalance.

Low dose carvedilol will be considered effective if the 1-df test in the linear model is significant and the expected LV T-D z-score is lower for placebo at follow-up

time points, indicating the effectiveness of low-dose carvedilol in preserving LV T-D.

In addition to unadjusted analyses which are appropriate under the randomization principle, adjusted analysis will also be performed. Significantly imbalanced covariates and covariates known to be prognostic for HF, such as age at anthracycline exposure, chest irradiation, and time from completion of treatment, will be incorporated in the longitudinal models before including and testing the time by treatment group interaction.

To address potential noncompliance, we will also conduct an as-treated analysis, considering patients' actual treatment uptake. Instead of the treatment indicator (placebo or carvedilol), we will include adherence rate, i.e. 0 for placebo and a number between 0 and 1 for carvedilol determined by pill count, in the linear mixed effects model. Time-specific adherence rate and the overall adherence rate will be considered. If carvedilol is effective, we may expect to see an increase in LV T-D z-score and a greater difference in slope with increasing adherence rate.

The estimates from linear mixed effects model are valid in the presence of incomplete response data if missing data occurs at random. However, nonparticipation and dropouts may occur differentially between treatment groups for various reasons, possibly resulting in non-ignorable missing data. In addition to collecting information on reasons for nonparticipation, we will apply two analytic approaches to examine the effects of missing data on study results:¹²⁵ 1) pattern mixture models and 2) selection models. In pattern mixture models, the 16 possible missing data patterns (arising from 4 follow-up time points, with no missing data at t₀, and considering a response as missing if data from echocardiographic assessment are missing) will be used as covariates in the above-described bivariate linear mixed effects model. The effects of missing data on the estimate of treatment effect can be assessed. An overall estimate of the treatment effect may be obtained by averaging the estimates over the missing pattern groups. In the selection model, we will model the probability of dropout using baseline covariates to estimate the propensity for dropout. The propensity scores will be used as a covariate in the bivariate linear mixed effects model to adjust for the effects of dropout on treatment effects.

Secondary echocardiographic efficacy measures (afterload, systolic and diastolic measurements) will be evaluated by applying the same methods for longitudinal analysis. Significance of the carvedilol effects will be evaluated in the manner described above based on testing the significance of the interaction of time by group indicator variables. The distribution of continuous variables will be examined graphically and appropriate transformations made before applying analytical methods based on normal assumption.

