3.1.6 Randomization

Randomization will occur after enrollment and must be completed within 45 days of the eligibility screening. If randomization and enrollment are taking place on the same day, then randomization can take place before enrollment. This will allow ample time for the pharmacist to receive the kit assignment.

If eligibility screening procedures were completed on multiple days, patients must be randomized within 45 days of the first day.

Randomization will take place through a third party drug distributor called "Sharp Clinical Services" (Phoenixville, PA). See the "Study Drug Packet" on the ALTE1621 web page on the COG website for details on timing and randomization through the IVRS system.

Sharp Clinical Services will randomize the subject to carvedilol or placebo using a blocked, stratified randomization design with age at diagnosis (2 strata: < 5 years, ≥ 5 years), time since diagnosis (2 strata: < 10 years, ≥ 10 years), and cardiac irradiation (2 strata: any, none), as stratification factors (8 strata total) and a block size of 4 to balance the number of participants in each arm. Blinded study drug will then be assigned to the patient. City of Hope, the coordinating center, will be notified that randomization is complete.

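### The deciding slope test leaves out the three stratification factors, and an imbalance-triggered sentence just before the efficacy rule can be read as changing its covariates

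*Combined protocol and SAP*

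**What the plan says.** - **Randomisation.** Section 3.1.6 describes allocation "using a blocked, stratified randomization design with age at diagnosis", together with time since diagnosis and cardiac irradiation: eight strata, blocks of 4. Section 9.1 repeats this ("Randomization will be stratified by age at diagnosis").
- **Deciding test.** Section 9.3.1 models the LV T-D z-score linearly in time and says "Treatment effect will be tested by a 1-df test for the interaction". It names no covariate for that test. The efficacy rule is "Low dose carvedilol will be considered effective if the 1-df test in the linear model is significant", with the placebo z-scores lower at follow-up.
- **Imbalance check.** Between the two, 9.3.1 compares the arms on age at anthracycline exposure, chest radiation and time from treatment, and on "study site, as well as the mean LV T and D z-scores at baseline". It then says "If imbalance is evident, our analysis will take into account the covariates with significant imbalance". No significance level is given.
- **Adjusted analysis.** After the efficacy rule comes "In addition to unadjusted analyses which are appropriate under the randomization principle, adjusted analysis will also be performed". Its covariates are "Significantly imbalanced covariates and covariates known to be prognostic for HF". The examples are chest irradiation, age when anthracyclines were given and time since treatment ended. No covariate-by-time terms are stated.
- **Elsewhere.** Under Aim 1.2.2, the stratification categories for radiation and age are used only to look for effect modification. Time since diagnosis is not listed there.

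**The concern.** A trial that stratifies its randomisation would normally analyse by the same factors. Here the test is on slopes, so the terms that matter are factor-by-time interactions. The plan has these neither in the deciding test nor, as far as it states, in the adjusted analysis.

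The imbalance sentence adds a second difficulty. Imbalanced covariates are assigned twice: once to an unspecified main analysis immediately before the efficacy rule, and once to the additional adjusted analysis. Nothing in 9.3.1 says which model decides if the two disagree. If the first assignment is taken literally, the deciding model depends on which baseline variables happen to differ between the arms. Two of those variables, baseline LV T and D, are components of the outcome, and baseline LV T-D is already the first of the five repeated measurements.

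At stake are a small amount of precision and a deciding model that is not fully fixed in advance.

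**Working it through.** **1. The plan's own figure.** Inputs from Section 9.4 (Amendment #4): 91 per arm, SD 1, 19% attrition per year, compound symmetry, two-sided 0.05, power 0.80. Use the linear contrast c = (-2, -1, 0, 1, 2) and an arm difference of d·k/4 at visit k, so the contrast of the differences is 2.5d.

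- n_k = 91 × 0.81^(k/2) = 91, 81.9, 73.7, 66.3, 59.7
- Var = 2 ΣΣ c_k c_l ρ_kl / √(n_k n_l) = 0.1151 at correlation 0.6, so SE = 0.339
- d = (1.960 + 0.842) × 0.339 / 2.5 = 0.380

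| Correlation | 0.6 | 0.7 | 0.8 | 0.9 |
|---|---|---|---|---|
| Table 4 | 0.38 | 0.34 | 0.28 | 0.21 |
| Recomputed | 0.380 | 0.333 | 0.278 | 0.208 |

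Table 4 therefore matches a slope contrast without covariates, and it stands.

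**2. Strata-by-time terms.** The documents do not say that the strata affect slope, so a range is assumed. The simulation used 182 patients, five visits, linear 19% per year attrition, correlation 0.7, eight strata with blocks of 4, and REML with random intercept and slope. Assumed: factor prevalences 35/50/30%, a level effect of 0.2 SD per factor, and residual slope variance 0.02 per year squared. There were 4,000 runs per cell. Power at a 24-month difference of 0.34, common baseline:

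| Slope shift per factor (z/yr) | 0 | 0.05 | 0.067 | 0.1 | 0.2 |
|---|---|---|---|---|---|
| No strata | 76.7% | 76.5% | 76.7% | 76.0% | 68.7% |
| Strata main effects | 77.0% | 77.0% | 77.7% | 77.1% | 72.0% |
| Strata and time interactions | 76.5% | 77.2% | 77.9% | 77.9% | 77.0% |
| Gain, last row minus first (points) | -0.2 | 0.7 | 1.2 | 1.9 | 8.3 |

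The Monte Carlo SE is 0.7 points. At 0.067 the extreme strata differ by 3 × 0.067 = 0.2 z per year, which is the whole placebo decline projected in Section 9.4. At 0.2 they differ by 0.6, which is extreme. The unadjusted and strata-by-time tests disagree on significance in 1.8%, 3.0%, 3.4%, 4.5% and 10.3% of trials across the columns.

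**3. How often the trigger fires.** Each check is taken at 5% (assumed). Stratification largely balances the relatives of the strata, which leaves site, LV T and LV D. If these were independent, 1 - 0.95³ = 14.3%. Simulation with 15 equal sites (assumed) and LV T-D component correlations of 0, 0.5 and 0.8 gives 13.6%, 12.7% and 12.6% overall. Of this, a stratum relative accounts for 0.2-0.4%, site for about 4%, and baseline LV T or D for 9.5%, 8.5% and 8.1%.

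**4. What it does when it fires on a baseline component.** 1,500 null runs per cell, conditional on significant imbalance in a covariate correlated 0.5, 0.7 or 1.0 with baseline LV T-D, without stratified randomisation. Shift in the 24-month difference (z), against the arm that started higher:

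| Model | Without the covariate | With it |
|---|---|---|
| Common baseline | 0.000 / -0.003 / 0.004 | -0.043 / -0.065 / -0.082 |
| Treatment main effect fitted | -0.046 / -0.069 / -0.090 | -0.046 / -0.069 / -0.097 |

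Repeat runs agree in direction, with somewhat smaller common-baseline shifts at the higher correlations. Against the projected 0.4, 0.04 to 0.08 is 10-20%. With a treatment main effect, the covariate makes essentially no difference.

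**5. Treatment main effect.** Section 9.3.1 does not say whether one is fitted. Under generalised least squares with 91 per arm and compound symmetry, a common baseline lowers the variance of the slope difference by 16.5%, 11.7%, 7.4% and 3.5% at correlations 0.6 to 0.9. At 0.7, for example, it falls from 0.00373 to 0.00329. In the simulations of step 2, fitting or omitting this term changed significance in 7.7-9.2% of trials.

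**The case against.** The strongest reply is that the unadjusted test is already decisive. It is defined without covariates, the efficacy rule refers back to it, the adjusted analysis is described as additional, and Table 4 is a covariate-free calculation. That is the better reading, and a reader who concludes that the primary analysis is certainly data-driven goes beyond the text. What remains is that, on this reading, the imbalance sentence before the efficacy rule does no work, so deleting it loses nothing.

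A second reply is that omitting the strata is a matter of preference: the gain is small, and close relatives of all three factors are already adjusted for. The gain is indeed small. But the relatives are not the factors as randomised, and without time interactions they barely affect a slope test.

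A third is that the shift in step 4 depends on the model. This is correct. It also follows the direction of the chance imbalance, so it averages out over randomisations. Conditional rejection rises by 0.7 to 3.1 points (5.9/5.4/5.3% to 6.6/8.0/8.4%), which over 8-10% of trials is about 0.1 to 0.3 points. A reader might infer inflated type I error from this, but the figures do not support that.

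Two limits also stand. The simulations use REML, while 9.3.1 permits GEE and Appendix II calls the main model GEE. And if the LV T and D wording is a slip for LV T-D, there is one such check at 5%, not two.

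**Conclusion.** The point holds, at modest size. The deciding test omits the factors used to randomise, and one sentence leaves room for chance imbalance to change its covariates.

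- **Strata.** About 0 to 2 points of power for plausible stratum effects on slope, with no measurable loss if there are none. Larger gains need strata that explain an implausibly large part of the decline.
- **Trigger.** A shift of about 0.04-0.08 z arises only in a common-baseline model and only when a baseline component triggers entry, roughly 8-10% of trials at the assumed 5% level.
- **Treatment main effect.** Leaving this unstated matters at least as much as the strata, since it alone changes significance in about 8-9% of simulated trials.

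The documents do not support the stronger inferences that the sample size is wrong, that Table 4 is wrong, or that the false-positive rate is raised. The sizes rest on assumed prevalences, slope effects, number of sites and imbalance level, none of which the documents give.

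**What to change.** In Section 9.3.1, before the final unblinded comparison:

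1. Name one deciding model: LV T-D z-score on time and time-by-treatment, plus the three stratification factors as randomised and their time interactions.
2. State whether a treatment main effect is fitted. A common baseline mean matches the plan's own expectation of no difference at t0.
3. Delete the imbalance-triggered sentence, and remove significantly imbalanced covariates from the adjusted analysis.
4. Do not enter baseline LV T, D or T-D as covariates, because baseline is already a repeated measurement.
5. Keep the unadjusted and prognostic-covariate models as sensitivity analyses.

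The change uses variables already collected for randomisation and adds six parameters (three main effects, three time interactions) for 182 patients. Where the strata have no effect on slope, simulated power is 76.5% with them and 76.7% without. The sample size does not change. The Amendment #4 futility analysis (Section 9.5.2, Table s3) can be reported under the model used at that time, with a sentence noting the difference.

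If the team prefers the unadjusted test, the minimum is one sentence naming it as decisive, with the trigger deleted. That settles which model decides but leaves the analysis without the randomisation factors.
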